Research subjects will be persons with T1D who are using continuous glucose monitoring (CGM) with Dexcom G6 and either an insulin pump or multiple daily injections (MDI) with long-acting insulin (insulin glargine U100) administered in the morning. Recruitment will take place from our Washington University-Barnes Jewish Hospital Diabetes Center, which cares for over 1200 persons with T1D per year. Availability of medical records is considered key to appropriate patient selection and follow-up of any adverse events, thus persons outside of our system will not be recruited for the study. Participants must be able to use a smart phone with applications for their CGM device, insulin pump (if using) and the Biosense BKA device. The inclusion and exclusion criteria are listed below. Every effort will be made to recruit participants across the age range of the study, and to include persons of both genders and of different races and ethnicity, based on our local population.

Inclusion criteria:

- Type 1 diabetes for >1 year
- Age 18 75, any gender, race or ethnicity
- HbA1c <10%
- Stable insulin delivery method for the past 30 days
- Vision of 20/40 or better, including ability to read all device instructions and insulin pump settings
- Use of an insulin pump and ability to make adjustments to pump settings
- Insulin delivery by MDI with basal insulin (glargine U100) given in the morning OR willingness to transition to basal glargine given in the morning for at least 48 hours prior to insulin withdrawal visits
- Use of personal CGM, only Dexcom G6 will be permitted for data consistency
- Use of cellular phone (iOS11 and above or Android) with data capability with connectivity to Dexcom Clarity app and Biosense Ketone Monitoring app
- Willing to share CGM, capillary ketone results and BrACE data with the study group
- Able to understand the study requirements, risks and benefits and able to provide written informed consent
- Able to schedule the visits and perform study related tasks

Exclusion criteria:

- History of DKA in the past 6 months, or more than 1 episode of DKA in the past 2 years
- Use of insulin degludec, insulin glargine U300 or insulin detemir as basal insulin and unwilling to transition to glargine given in the morning for at least 48 hours before the insulin withdrawal visits
- Use of an SGLT2i in the past 30 days or intolerance to SGLT2i use in the past for any reason

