- Segment 1 will consist of 2 weeks of usual care with participants measuring fasting and random breath ketones paired with capillary BOHB (Group A) or usual care plus dapagliflozin with participants measuring fasting and random breath ketones paired with Capillary BOHB (Group B). Participants will be instructed to do paired ketone testing anytime their glucose is >250 mg/dL, or if they develop symptoms of feeling unwell for any reason.
- 3. Visit 2 will be a single day of on-site close monitoring during insulin withdrawal. Morning insulin doses will be withheld, and the participants will have hourly checks of glucose, capillary BOHB, breath ketones, blood BOHB and acetoacetate. CBC will be done at baseline, and BMP to check electrolytes will be done at baseline and every 2 hours until the study end. Instructions for Segment 2 will be provided and recommendations for change in insulin regimen or insulin doses will be made at this visit.
- 4. Segment 2 will consist of 2 weeks of usual care (Group B) or usual care plus therapy with dapagliflozin SGLT2i (Group A). Participants will be instructed to do paired ketone testing fasting and randomly during the day, and if their CGM glucose exceeds 250 mg/dl or if they feel unwell.
- 5. Visit 3 will be a single day of on-site close monitoring during insulin withdrawal (Group B), but after taking an SGLT2i tablet (Group A). Morning insulin doses will be withheld, and the participants will have hourly checks of glucose, capillary BOHB, breath ketones, blood BOHB and acetoacetate. CBC will be done at baseline, and BMP to check electrolytes will be done at baseline and every 2 hours until the study end.

The study design and schematics are depicted below:

	Phone								Visit 3 /FOS
GROUP A	or clinic visit	Visit 1	Gap d	Usual Care + Ketone Monitoring	Visit 2 IRU Insulin Withdrawal	Gap e	Optional Visit	Usual Care + SGLT2i + Ketone Monitoring	IRU Insulin Withdrawal
		On-site		HOME- Segment 1 14 +/-2 days	On-site		Phone or on-site	HOME - Segment 2 14 consecutive	On-site
Phone screening	х								
Informed Consent discussion	Х	Х							
Informed Consent	X	X							
Demographics, medical, medication and		v							
Vital signs, height, weight		×							
Inclusion/exclusion review	x	x							
Physician H&P	~	X							
Near Vision Accuity Screening		x							
CGM check for connectivity to clinic		X							
Dispense capillary ketone meter and									
supplies, breath ketone analyzer		X							

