#### On-site Visit

The on-site will be conducted at the Intensive Research Unit at Washington University. Patients will be asked to arrive fasting, to stop their basal insulin delivery 1 hour before arrival at the center if on an insulin pump or to hold injectable insulin doses. Prior to leaving home, the participant's blood glucose should be 90 – 250 mg/dL, and BOHB <1.5 mmol/L, or the test day will be rescheduled. Time of the last insulin dose will be recorded. Vital signs and baseline labs including a CBC, BMP and pregnancy test in women with child-bearing potential will be done. Measurements of capillary BOHB using the Precision Xtra meter and BrACE using the Biosense BKA will be done hourly X7 or 8 if the patient remains relatively asymptomatic, and the capillary BOHB level does not exceed 4 mmol/L. If the capillary BOHB reaches 2.5 mmol/L or capillary glucose reaches 250 mg/dL, the capillary finger sticks and breath measurements may be collected at 30 minute intervals. The venous blood samples will continue to be collected on the hour intervals. Venous blood samples for BMP, BOHB and AcAc\* will be drawn at baseline and every 2 hours X3 plus the end of the study.

The insulin withdrawal portion of the study will end (stopping rules) upon patient request for any reason, if the patient becomes symptomatic with nausea or vomiting (even if he or she does not request that the study be stopped), after 7 hours of fasting without insulin, or if either the capillary BOHB is  $\geq$ 4 mmol/L or the CGM blood glucose is  $\geq$ 400 mg/dL. BMP will be done every 2 hours and at the end of the study. At the termination of the ketogenic fast, participants will be given a correction dose of rapid acting insulin subcutaneously or regular insulin IV, per investigator discretion. They will then restart insulin via insulin pump, or administer both basal and mealtime insulin via subcutaneous injection and be given a standard meal. Participants will be observed for a minimum of 1 hour after the study end for return to near normal metabolic status. An additional contact by phone or other means in the evening will be made to confirm safety and no adverse consequences of the study day.

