#### On-site visit, SGLT2i

The on-site visit with SGLT2i will be conducted at the Intensive Research Unit at Washington University, the same format as described for usual care. Patients will be asked to arrive fasting, to stop their basal insulin delivery 1 hour before arrival at the center if on an insulin pump or to hold injectable insulin doses. Prior to leaving home, the participant's blood glucose should be 90 – 250 mg/dL, and BOHB <1.5 mmol/L, or the test day will be rescheduled. Time of the last insulin dose will be recorded. Patients will be given a dose of dapagliflozin, 10 mg upon arrival at the IRU. Vital signs and baseline labs including a CBC, BMP and pregnancy test in women with child-bearing potential will be done. Measurements of capillary BOHB using the Precision Xtra meter and breath ketones using the Biosense BKA will be done hourly X7 if the patient remains relatively asymptomatic, and the capillary BOHB level does not exceed 4 mmol/L. If the capillary BOHB reaches 2.5 mmol/L or capillary glucose reaches 250 mg/dL, the capillary finger sticks and breath measurements may be collected at 30 minute intervals. The venous blood samples will continue to be collected on the hour intervals. Venous blood samples for BMP, BOHB and AcAc\* will be drawn at baseline and every 2 hours X3 plus the end of the study.

The insulin withdrawal portion of the study will end (stopping rules) upon patient request for any reason, if the patient becomes symptomatic with nausea or vomiting (even if he or she does not request that the study be stopped), after 7 hours of fasting without insulin, or if either the capillary BOHB is  $\geq$ 4 mmol/L or the CGM blood glucose is  $\geq$ 400 mg/dL. BMP will be done every 2 hours and at the end of the study. At the termination of the ketogenic fast, participants will be given a correction bolus dose of insulin by IV or subcutaneous injection, restart insulin via insulin pump, and or administer an injection of pre-meal insulin and be given a standard meal. Participants will be observed for 1 hour or more if needed after the study end for reduction in ketones and glucose into safe ranges. Glucose and ketone monitoring will continue into the evening with a phone call or other contact made with the patient for safety.

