#### Assessment of Safety

Safety parameters will be analyzed separately for the usual care segments and for the insulin withdrawal days. For the usual care segment, the main safety concern is a level of capillary blood BOHB >1.5 mmol/L at any time. Participants will be asked to call the study coordinator or investigator for advice if this happens, and to start a ketone action plan. The participant can call for concerns about any level of capillary BOHB during the study, but in particular while taking an SGLT2i. The participant will be

provided with a ketone-action plan that will include ingestion of carbohydrates, fluid and insulin administration and frequent follow-up testing. The study investigator will monitor the participant with contact every 1 - 2 hours until the episode resolves. Any capillary blood BOHB level >1.5 mmol/L will be reported as an event of special interest, with follow-up ketone action plan results noted. BrACE levels of >15 without corresponding BOHB level >1.0 mmol/L will be considered likely due to contamination and repeated in 1 hour. Likewise, any severe hypoglycemia event will be reported as an adverse event. Patients with level 2 hypoglycemia, glucoses <54 mg/dL for more then 1% of the day on weekly CGM reviews will have insulin doses adjusted and a discussion with the investigator.

The most important safety parameter of the insulin withdrawal test days will be capillary blood BOHB levels >3 mmol/L, or symptoms of nausea or vomiting at any level of BOHB. Capillary BOHB level of >3 mmol/L constitutes a stopping point for the insulin withdrawal study, and immediate treatment with fluids, insulin and carbohydrates will be commenced, and the patient followed on-site until the episode resolves. Resolution will be defined as cessation of symptoms and capillary BOHB level <1.0 mmol/L, with blood glucose <250 mg/dL. Note that in a similar study of insulin withdrawal before and after treatment with the SGLT2i, canagliflozin, it took about 6 hours for glucose to increase from 100 to 300 mg/dl (pre-treatment) and from 100 to 220 mg/dL with canagliflozin. During the six hours, BOHB increased from 0.2 to 1.2 mmol/L (pre-treatment) and from 0.4 to 1.5 mmol/L with canagliflozin. This proposal uses a similar time sequence, and thus we anticipate similar results from the insulin withdrawal.

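### The two on-site visit sections give different end-of-withdrawal insulin instructions for injection users, and the dapagliflozin section does not say whether the withheld basal dose is restored

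*Combined protocol and SAP*

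**What the plan says.** MDI users are eligible. The inclusion criteria under Research Design list "Insulin delivery by MDI with basal insulin (glargine U100) given in the morning", or willingness to move to that schedule for at least 48 hours before the withdrawal visits. The descriptions of Visit 2 and Visit 3 in the same section both state: "Morning insulin doses will be withheld".

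The end of withdrawal is then described twice:

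- **No-drug day (On-site Visit).** After a correction dose, participants restart the pump, or they "administer both basal and mealtime insulin via subcutaneous injection and be given a standard meal". Then: "Participants will be observed for a minimum of 1 hour after the study end for return to near normal metabolic status". Contact follows in the evening.
- **Dapagliflozin day (On-site visit, SGLT2i).** The visit is said to have "the same format as described for usual care". Injection users are again told "to hold injectable insulin doses". After a correction bolus, participants "restart insulin via insulin pump, and or administer an injection of pre-meal insulin and be given a standard meal". They are observed for an hour, or longer if needed, until ketones and glucose are in a safe range, for which no figures are given. Glucose and ketone monitoring runs into the evening, with a contact.

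Assessment of Safety gives the only numbers: "Resolution will be defined as cessation of symptoms and capillary BOHB level <1.0 mmol/L, with blood glucose <250 mg/dL". They follow a sentence that makes capillary BOHB above 3 mmol/L a stopping point. Both on-site sections stop at 4 mmol/L or more.

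**The concern.** The dapagliflozin section does not simply refer back to the usual-care section. It writes the procedure out again, and at this step the mealtime component is kept while the basal component is missing. Staff working from that section could take the difference as intended, or could take it as loose drafting. The phrase joining pump restart and pre-meal injection does not separate pump users from injection users, so it does not help them decide.

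Pump users regain basal delivery when the pump restarts. Injection users do not, unless someone gives the dose. The silence therefore falls on the group for whom an explicit instruction matters most. It also falls on the day on which the protocol's third hypothesis expects higher ketones.

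The second difficulty is when observation may end. The two days use different descriptions, neither with figures, and the section that has figures attaches them to a different stopping threshold. It is unclear which participants the numeric definition covers.

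**Working it through.** No arithmetic decides this point; it rests on comparing the texts.

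**1. Is basal insulin withheld on both days?** Yes. Morning glargine is the MDI schedule before the visits, and both visit descriptions and both on-site sections withhold morning or injectable insulin.

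**2. What is restored, and when does observation end?**

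| Step | On-site Visit (no drug) | On-site visit, SGLT2i |
|---|---|---|
| Correction insulin | Yes | Yes |
| Pump users | Restart pump | Restart pump |
| Injection users, mealtime insulin | Named | Named |
| Injection users, basal insulin | Named | Not mentioned |
| Minimum observation | 1 hour | 1 hour, longer if needed |
| Aim of observation | Near-normal metabolism, no figures | Ketones and glucose in a safe range, no figures |
| Evening | Contact | Glucose and ketone monitoring, plus contact |

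The basal row is a difference in the insulin instruction. The aim row is a difference in the criterion for ending observation.

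**3. Does another section settle the basal question?** No. The schedule tables for Groups A and B carry one row for correction insulin, with or without fluids, on both test days; basal insulin is not named. The row on basal adjustment for MDI users is marked at Visit 1 only. Assessment of Safety prescribes fluids, insulin and carbohydrate when its stopping point is reached, without saying which insulin and without distinguishing the two days.

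**4. Whom does the numeric definition of resolution cover?** Assessment of Safety names two main concerns on withdrawal days: capillary BOHB above 3 mmol/L, and nausea or vomiting at any BOHB level. The definition includes cessation of symptoms, so symptomatic stops can reasonably be read as covered. Three situations are unclear:

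- A BOHB above 3 but below 4 mmol/L is a stopping point under Assessment of Safety and not under the on-site sections.
- A symptom-free participant who completes 7 hours at, say, 2.9 mmol/L has not passed the threshold to which the definition is attached.
- A symptom-free participant stopped for glucose of 400 mg/dL or more, with BOHB not above 3, is in the same position.

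**5. Are the planned analyses affected?** The Statistics section compares withdrawal days on the frequency of venous BOHB above 1.5 mmol/L during withdrawal, and on the slope and intercept of capillary BOHB against time from withdrawal. It also correlates breath acetone with BOHB during withdrawal. Rescue insulin and discharge come after those measurements. The sample-size statement for the withdrawal days does not depend on them either. The difference between 3 and 4 mmol/L is used here only for its bearing on the numeric definition.

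**The case against.** The strongest reply is that the dapagliflozin section declares the same format, so the earlier steps carry over and the missing word is a drafting slip. That reading is available, and nothing in the section forbids a basal injection. But the section goes on to restate this very step differently, so the general statement does not reliably override the specific one.

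A second reply is that the dapagliflozin day is otherwise at least as well protected: observation may be extended, its aim names both ketones and glucose, and monitoring continues into the evening. This stands, and it rules out describing discharge as unmonitored. It does not say what happens to the basal dose.

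Several stronger readings are tempting and are not supported:

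- **That MDI participants on dapagliflozin are sent home without their basal insulin.** This is an inference from silence; no section says so.
- **That the wording biases the drug comparison.** Rescue follows the withdrawal measurements, no between-condition comparison of post-test ketosis is planned, and adverse events are simply tabulated.
- **That the basal interval becomes about 48 hours (2 × 24) rather than about 31 to 32 (24 plus a 7 to 8 hour test).** This assumes the next dose waits until the following morning. The documents do not say so, and they require morning glargine only before the visits for those who switched.
- **That the expected 1.5 mmol/L at six hours on an SGLT2 inhibitor shows a special problem on the drug day.** The same paragraph gives 1.2 mmol/L without drug, also above the 1.0 mmol/L resolution mark. Both come from a canagliflozin study and describe withdrawal, not the period after rescue.

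**Conclusion.** The inconsistency holds. For injection users, basal insulin is named at the end of the no-drug day and left unaddressed at the end of the dapagliflozin day, although it is withheld on both and the format is said to be the same. The criteria for ending observation also differ, and the numeric definition is attached to a stopping point that conflicts with the on-site sections.

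The basal question touches one of the two test days for each MDI participant. Their number is not given, so the count lies between 0 and the planned 20. The end-of-observation question can touch pump and MDI users on either day. No effect on the planned withdrawal-day estimates is claimed. The point matters for participant safety and for uniform conduct, and it should be corrected because the text as it stands permits two different practices. The conclusion assumes only that staff may follow each section as written. No view is taken on which instruction or threshold is clinically right.

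**What to change.** Reconcile On-site Visit, On-site visit, SGLT2i and Assessment of Safety into one end-of-withdrawal paragraph that both test days refer to. It should:

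- treat pump users and MDI users separately;
- state what happens to the withheld basal insulin;
- use one consistent criterion for ending observation, and say to which stopping reasons it applies;
- cite one BOHB stopping point, the same in all three sections.

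If the investigators intend the two days to differ, the paragraph should say so and give the reason, and the statement that the format is the same should be qualified. The clinical content is for the investigators to decide.

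The cost is a wording amendment and, depending on the criterion chosen, longer on-site stays for some participants. Sample size and planned analyses need no change on this account.

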This proposed study of 4 distinct segments that include routine testing of ketones during usual care, during insulin deficiency, and while taking a SGLT2i in addition to usual care, then with insulin deficiency **after the SGLT2i has reached steady state** and ingested that morning. We will study 20 adults with T1D who are using Dexcom G6 continuous glucose monitor (CGM), plus any form of insulin delivery. Study participants will be randomized to Group A or Group B as shown below in Figure 1. Simultaneous ketone monitoring using a the Biosense® BKA and capillary blood BOHB measurement will be done 2-3X daily for 2 weeks during each of the outpatient segments. This will generate >800 data points comparing breath acetone, measured in units called ACEs, versus capillary blood BOHB measurements for each 2 week period. On days of insulin withdrawal, which will take place on the Washington University Intensive Research Unit (IRU), frequent monitoring with capillary blood measurements of BOHB (Precision Xtra®, Abbott) will be compared with breath BrAce measurements (Biosense®, Readout) and laboratory measurements of BOHB and acetoacetate. Electrolytes and glucose will also be measured. The schematic is shown below:

Figure 1. Study plan and study groups.

The goals of the study are to better understand ketone fluctuations in persons with T1D during usual care and when taking a SGLT2i in addition to usual care through frequent ketone monitoring. Additional information about usability of the breath ketone analyzer will be tested with simple questions using a Likert scale and a structured interview at the end of the study. The question is not whether the ketone measurements correlate perfectly with the gold standard BOHB measurements, but whether breath ketone measurements by the Biosense BKA are adequate for patients to understand their "ketone status" and identify states of rising ketones early enough for mitigation strategies to work. The potential advantages of using a breath analyzer are that it is non-invasive; it is easy to use repeatedly without additional cost or pain from fingersticks, and it may be sufficiently informative to employ a ketone action plan before ketones rise to hazardous levels.

The long term goals of this study extend beyond the completion of the study to the development of DKA mitigation strategies that are manageable and accepted by patients. A ketone mitigation strategy must

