# Methodology

# **Research Design**

This study is a single-center, investigator-designed and led clinical trial testing the efficacy of the breath ketone analyzer, Biosense, for the detection of ketogenesis during four distinct study periods, which will allow comparisons of the Biosense measured breath ketones with capillary BOHB and both of these point of care (POC) tests with laboratory measured BOHB and acetoacetate (AcAc). Ethics approval will be from the Washington University Human Studies Protection Office, and obtained prior to contact with any potential participant. Participants with T1D using a stable form of insulin delivery, either insulin pump or multiple daily injections (MDI) and will perform paired measurements of capillary BOHB and BrACE during usual care or usual care plus therapy with a SGLT2i. Paired testing will then be done during insulin withdrawal in usual care and insulin withdrawal while taking a SGLT2i that has reached steady state.

Participants will be randomized to Group A, in which the usual care segment and insulin withdrawal day is done first followed by the usual care plus SGLT2i and insulin withdrawal with SGLT2i or Group B, in which the SGLT2i will be taken during usual care for 2 weeks, then insulin withdrawal with SGLT2i followed by usual care for 2 weeks then insulin withdrawal during usual care. The study design is robust, and will allow more than 800 paired measurements of breath ketones with capillary BOHB during usual care, more than 800 paired measurements during usual care plus SGLT2i therapy. Additionally, due to concerns about ketogenesis during times of insulin deficiency, and the demonstrated increase in ketone generation with SGLT2i therapy, the pair-wise comparisons will be informative about the correlation of BrACE as measured with the Biosense device with POC and laboratory BOHB measurements and laboratory measured AcAc.

Dapagliflozin, 10 mg was selected over the other FDA approved SGLT2i drugs because this dose was used in the recently published study, DAPA-CKD, which showed remarkable reduction in progression of

kidney function decline in persons with and without T2D, HR 0.61 (95% CI, 0.51 - 0.72). Reduction in the progression of diabetic kidney disease is a high priority for persons with T1D. In the study procedures, SGLT2i refers to dapagliflozin, 10 mg daily.

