After the investigator or sub-investigator determines that the participant meets all of the inclusion and none of the exclusion criteria, the study team will proceed with interrogation of the participant's CGM to ensure appropriate connectivity with the study team. Participants will be asked to demonstrate competency in making changes to insulin pump settings. The study team members will train the participant in the use of the Precision Xtra ketone meter and the Biosense BKA. Participants will be instructed to wait 60 minutes after eating, smoking/vaping, drinking sodas or flavored waters or consuming items such as toothpaste, mouthwash, cough drops, breath mints, chewing gum, lip balm and artificial sweeteners before doing a BrACE measurement. If using alcohol, participants should wait 4 hours before testing with the BKA. Participants will be instructed in avoidance of environmental contaminants also. Participants will be able to test capillary BOHB even when conditions are not optimal for BrACE.

The participant will upload the Biosense app onto his or her smart phone and test a test run will be conducted. A diary will be provided for entry of BOHB ketone measurements and BrAce with space for comments in case of known interference with BrAce or other problems with measurements. A written ketone action plan will be provided to all participants in the study. Participants will be informed that they may stop participating in the study at any time without loss of usual care of their diabetes.

A ketone action plan will be provided to each participant that will include the following elements: ingestion of carbohydrates, fluid intake and insulin administration with doses of insulin adjusted according to individual requirements. Participants will be asked to employ the ketone action plan if BOHB reading is >1.5 mmol/L. BrACE levels of >15 in the absence of corresponding BOHB level >1.5 mmol will be considered due to contamination and the participant will be asked to repeat the levels in 1 - 2 hours.

Patients will be randomized by card draw in lots of 4 to Group A or Group B

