Other adverse events, such as genital mycotic infections, urinary tract infections, orthostatic dizziness or any other acute or worsening illness will be reported. Study fatigue resulting in termination of the study will also be reported.

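### Planned adverse-event follow-up after the last dapagliflozin dose depends on sequence: none beyond the same evening in Group A, a review at least 12 days later in Group B

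*Combined protocol and SAP*

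**What the plan says.** The Research Design section sets two sequences. In Group A, "the usual care segment and insulin withdrawal day is done first followed by the usual care plus SGLT2i and insulin withdrawal with SGLT2i". In Group B, "the SGLT2i will be taken during usual care for 2 weeks, then insulin withdrawal with SGLT2i followed by usual care for 2 weeks". Under On-site visit, SGLT2i, a dapagliflozin tablet is given on arrival, so that visit carries the last dose in either sequence.

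After that visit the same section plans on-site observation of at least an hour and then an evening contact: "Glucose and ketone monitoring will continue into the evening with a phone call or other contact made with the patient for safety". In the Group A schedule (Figure 2) this is the final column, Visit 3/EOS. In the Group B schedule it is Visit 2, followed by an optional gap of up to 2-3 weeks, a usual-care segment of 14 ± 2 days, and Visit 3. The row for adverse-event and medication review is marked at Visits 1, 2 and 3 and at the optional visit in both tables. Nothing is scheduled after Visit 3 in either.

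On which events count, Assessment of Safety says: "Other adverse events, such as genital mycotic infections, urinary tract infections, orthostatic dizziness or any other acute or worsening illness will be reported". It gives no collection window after the last dose and no rule linking an event to drug exposure. Adverse events are to be tabulated manually.

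**The concern.** In a two-sequence design each participant receives the drug once, and one would expect the opportunity to record its adverse effects to be the same whichever period it falls in. Here the opportunity after dosing stops is set by the sequence. A genital or urinary infection that starts, or is first mentioned, a week after the last dose would be asked about in Group B at Visit 3. In Group A nobody is scheduled to ask.

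A second gap follows. The safety section analyses usual-care segments and withdrawal days separately. A Group B event soon after the last dose falls in the gap or in the later usual-care segment, and nothing requires the table to show how recently the participant had taken the drug.

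At stake is the completeness of the adverse-event tabulation that goes to the DSMB, and through its report to the ethics office and the funder. The trial is small, so losing planned post-dose follow-up in about half of the participants matters for what an absence of late events would mean.

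**Working it through.** The documents state no length of adverse-event follow-up, so there is no planned figure to reproduce. The windows below come from the schedules.

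**Inputs**
- Participants: "We will study 20 adults with T1D who are using Dexcom G6 continuous glucose monitor (CGM" (Rationale).
- Allocation: "Patients will be randomized by card draw in lots of 4 to Group A or Group B" (Visit 1). The split within a lot is not stated. Assuming 2:2, five lots of 4 give 10 and 10.
- Last dose: Visit 3 in Group A, Visit 2 in Group B.
- Group B usual-care segment: 14 ± 2 days. Optional gap before it: 0 to 2-3 weeks (Figure 2 and its notes).

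**Step 1: planned window = last scheduled review or contact minus last dose**
- Group A: Visit 3 to the evening of Visit 3 = 0 days.
- Group B, no gap: 14 − 2 = 12 to 14 + 2 = 16 days.
- Group B, two-week gap: 12 + 14 = 26 to 16 + 14 = 30 days.
- Group B, three-week gap: 12 + 21 = 33 to 16 + 21 = 37 days.

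**Step 2: share without planned follow-up beyond the dosing day**

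10 / 20 = 50%, under the even-split assumption.

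**Step 3: what that costs in the chance of seeing a late event**

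Let p be the per-person risk of an event that appears after the last dose. The documents give no such figure, so a range is shown. The chance of at least one event among n followed is 1 − (1 − p)^n.

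| Assumed p | 10 followed | 20 followed |
|---|---|---|
| 2% | 0.18 | 0.33 |
| 5% | 0.40 | 0.64 |
| 10% | 0.65 | 0.88 |
| 20% | 0.89 | 0.99 |

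Put the other way, at p = 10% the chance of seeing none is 0.9^10 = 0.35 with 10 followed and 0.9^20 = 0.12 with 20.

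If no late event is seen, the one-sided 95% upper bound on p is 1 − 0.05^(1/n): 25.9% for n = 10 and 13.9% for n = 20.

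These figures treat an event as seen if a review is planned and missed otherwise, so they describe planned collection only.

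**The case against.** The strongest reply is that no documented conclusion changes. The six hypotheses concern ketone measurement and use of the analyzer. The SGLT2i contrasts in the Statistics section concern BOHB and BrACE, all measured in the home segments or on the withdrawal days. No comparison of adverse events between conditions is planned. This stands. A reader might infer that the imbalance biases a safety comparison of SGLT2i with usual care toward no difference, but the documents plan no such comparison.

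Second, Group A is not unobserved. Every participant has 14 days of ketone testing and CGM on drug, an adverse-event review at the SGLT2i withdrawal visit, and observation and contact afterwards. Recruitment is confined to the centre's own patients partly so that records are available for following adverse events. This also stands. A reader might conclude that late events can be seen in only half of the participants, but that is true only of planned, active collection. Records may reveal some Group A events, although no post-study check is scheduled and mild events may never be recorded. The same-evening end is itself inferred from the last scheduled contact, because no end of collection is stated.

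Third, the protocol does not say that drug events emerge after dosing stops, and it does not name late ketosis among its events. The exclusion for "Use of an SGLT2i in the past 30 days or intolerance to SGLT2i use in the past for any reason" is an eligibility rule and cannot be read as an adverse-event window. The reference to 30 days after completion, for pregnancy intention, likewise carries no contact. Both points stand, so the risks in the table are assumptions.

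Fourth, Group B's follow-up is mostly one retrospective review, because usual care has no mandated contact. True, but Group A has no such review.

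Finally, counting every post-dose event as SGLT2i exposure would, with no gap, absorb most or all of Group B's usual-care segment. That is a sound objection to such a rule, and the fix avoids it.

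**Conclusion.** The point holds as one of ascertainment. Planned adverse-event collection after the last dose is 0 days in Group A and 12 to 37 days in Group B, and nothing else in the documents closes that difference. About half of the participants have no planned follow-up for events that appear or are reported after the last dose. The one-half share assumes even allocation within lots of 4 and that all 20 complete. The detection figures also rest on assumed event risks. Events during the 14 days on drug are reviewed in both groups and are not affected.

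The consequence is a descriptive safety table whose completeness depends on sequence. No planned test, and neither the primary outcome nor the sample size, is touched. The point is worth acting on because the remedy is cheap.

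**What to change.** 1. Add one telephone adverse-event review to the Group A table about 14 days after Visit 3, within the 14 ± 2 days of Group B's usual-care segment.
2. In Assessment of Safety, state that events after the last dapagliflozin dose are listed in both groups as a separate after-SGLT2i category over that same window, with onset date and days since last dose. Group B's usual-care segment keeps its label; it is not reclassified as drug exposure. Recording onset dates also allows the common window to be applied when a gap puts Group B's review as late as 37 days.

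The cost is about 10 calls by existing staff, one table row, a sentence or two on tabulation, and a slightly later end of study for Group A. No dose, visit procedure or stopping rule changes.
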